Given that GBS-NN has been found to be [REDACTED] protect against infections with serotypes Ia, Ib, II, III and V. And taken together with the finding that high levels of naturally occurring antibodies against Rib and AlphaC [REDACTED] correlate with protection against invasive GBS disease in newborns, makes GBS-NN an ideal candidate for a GSB vaccine with an estimated coverage of 95% of clinical isolates and hence justifies clinical testing of the vaccine.

[REDACTED]

Based on the data derived from the dose ranging studies in mice, it is considered appropriate to commence dosing at 10µg in humans.

The present study will also investigate whether adding the adjuvant Aluminium hydroxide (Alhydrogel®) will improve the immune response, and this will be done in parallel with dosing of GBS-NN.

It is anticipated that dose escalation will occur with a five-fold increment. Dose escalation will only occur after review of safety data up to two weeks after vaccination. At this review a decision will also be made whether a booster dose is required (may be given 28 days after first vaccination).

In Part A, the first cohort will consist of 10 volunteers (8 active, 2 placebo) to receive a dose of 10µg without Alhydrogel®, the second and third cohorts may be dosed in parallel. Cohort 2 will receive a dose of 50µg, without Alhydrogel® and cohort 3 will receive 10µg GBS-NN with Alhydrogel®. Cohorts 4 and 5 may also be dosed in parallel with 250 µg without Alhydrogel® in cohort 4, whilst cohort 5 will receive 50µg with Alhydrogel®. The 6th cohort will receive 250µg GBS-NN with Alhydrogel®.

It is anticipated that the results from Part A will reveal where the optimal dose is likely to lie, and three dose regimens will be selected for evaluation in Part B. In Part B, each cohort will consist of 80 volunteers (60 active, 20 placebo)

It is expected that data accrued from the present study will allow the selection of the most appropriate dose to elicit the best immune response in humans. This dose will then be tested in pregnant women in subsequent studies with an expectation of 95% cover of GBS serotypes compared with 70% achieved with other vaccines.

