10. INVESTIGATIONAL MEDICINAL PRODUCT

10.1 Identity and Doses of IMP

The GBS-NN vaccine will be supplied [REDACTED]

[REDACTED]

[REDACTED]

[REDACTED]

[REDACTED]

In Part A, GBS-NN will be administered with and without Alhydrogel® (see table below for anticipated dose regimens). Cohorts in Part B may also receive GBS-NN without Alhydrogel® depending on the dosing regimens chosen. The procedure for the assembly of the different dose levels for Part A of the study is described in detail in the Pharmacy Procedure “Assembly of GBS-NN and placebo doses”. This procedure will be followed and, if required, amended to allow the assembly of additional dose strengths if indicated in Part B.

[REDACTED]

Individual volunteer treatments will be dispensed by the [REDACTED] pharmacist and labelled in accordance with Annex 13 of “The Rules Governing Medical Products in European Community, volume 4 Good Manufacturing Practice for Medicinal Products”.

The placebo vaccine [REDACTED]

[REDACTED]

It is currently anticipated that the following dosing strategy will be employed, however this may be modified, see below.

Part A:

Three dose levels will be selected, with and without Alhydrogel®: A, B, and C (where A is the lowest dose and C is the highest dose). It is anticipated that these doses will be 10µg, 50µg and 250µg, although these may be modified following ongoing review of data by the Safety Review Committee. The dose increase between cohorts will not exceed a five-fold increase.

It is anticipated that each cohort will receive the following dose regimen as described in the table below.

Note that cohort 7 is an optional cohort, and will proceed if deemed necessary to test an additional dosing regimen at a dose level below 250 µg, which will be determined following an ongoing review of the data.

Cohort	Dose schedule	Dose level	Adjuvant
1	Day 1, 29	10µg (A)	None
2	Day 1, 29	50µg (B)	None
3	Day 1, 29	10µg (A)	Alhydrogel®
4	Day 1, 29	250µg (C)	None
5	Day 1, 29	50µg (B)	Alhydrogel®
6	Day 1, 29	250µg (C)	Alhydrogel®
7	TBD	TBD, not exceeding 250 µg	TBD

Anticipated dose regimens in Part A

The aim of the dose finding overall is to identify the minimum dose level which provides the maximum immune response in terms of seroconversion rate, level of specific IgG reached and shortest time to peak level, whilst maintaining an acceptable safety profile.

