It is anticipated that the results from Part A will indicate whether the optimal dose level lies between 10µg and 50µg, or between 50µg and 250µg. The effect of Alhydrogel® on these parameters will guide the decision on whether to include it in one or more cohorts in Part B.

Part B:

The levels of GBS-NN specific IgG observed in Part A at Day 57, along with the safety profile, will be used to define a narrower range of dose levels to explore in Part B, where the group sizes are larger and the significance of any observed differences in immune responses will be measurable.

It is currently anticipated that three dose regimens will be selected for evaluation in Part B. At least two dose levels will be evaluated, which may be the same or different to those administered in Part A, but will not exceed the highest dose administered in Part A. It is anticipated that the regimens in Part B will comprise two doses of Alhydrogel® adjuvanted vaccine with the second being administered after a variable interval, not exceeding four weeks. It is, however, possible that a single dose of vaccine may be evaluated in Part B.

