12.2 Treatment Period and Post-Study Period

12.2.1 Part A

Volunteers will receive one of up to 7 dosing regimens of GBS-NN or placebo on 1 or 2 occasions – a primary dose will be administered at Visit 2 and volunteers will remain in the study unit for at least 8 hours post-dose, and if a booster dose is required, this will be administered at Visit 6. There will be a time interval of 4 weeks between Visit 2 and Visit 6, although this time interval may change if the dosing regimen is changed. There will be 10 volunteers in each group, 8 randomised to active and 2 to placebo. All cohorts in Part A will incorporate sentinel dosing of 2 volunteers in each cohort for the primary dose only: 1 on active treatment and 1 on placebo. No further volunteers in that cohort will be dosed until at least 24 hours after dosing the second volunteer, provided that there are no serious or unexplained safety issues as determined by the Investigator.

The decision to proceed with administration of the primary dose in subsequent cohorts will be made as described in Section 12.5.

The following assessments will be carried out at these visits:

Visit 2

A urine pregnancy test, brief physical examination, urine drugs of abuse test and alcohol breath test will be performed to confirm eligibility. Eligible volunteers will be randomised to receive active or placebo on 1 or 2 occasions (all volunteers will receive a primary dose at Visit 2 and a booster dose of the same medication (active or placebo) will be administered at Visit 6 if required). The dose administered, the number of doses and the time interval between doses will be dependent on the data generated from the preceding cohort and will be decided by the Safety Review Committee. A pharmacodynamic blood sample will be taken to measure pre-existing antibody levels prior to dosing. The primary dose will be administered at Visit 2 and volunteers will remain in the study unit for at least 8 hours post-dose. Vital signs will be recorded pre-dose and at 2 and 6 hours post-dose. A brief medical examination (including an assessment of the injection site) will be performed prior to discharge to ensure the volunteer is fit for discharge.

Visit 3

Visit 3 will be performed 24 hours (\pm 2 hours) after administration of the primary dose and an assessment of the injection site will be performed, vital signs will be recorded and AEs and concomitant medications will be reviewed.

Visit 4

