15.1.3 Inferential statistics

Adequate statistical tests will be used to carry out comparison between treatment/dose groups performed on primary, secondary or exploratory endpoints, even though it is accepted that the power of these tests for groups in Part A will be low due to small numbers of volunteers.

For categorical endpoints, such as local and systemic reactogenicity, a comparison of events intensity (scores) between vaccine dose groups will be performed with an adequate statistical test dealing with categorical variables (for example: Fisher exact test, Chi square test or generalized estimating equations).

For continuous endpoints, such as immune response induced by different GBS-NN vaccine dosing regimens, appropriate statistical method (for example: ANOVA) will be used to compare pre-vaccination and post-vaccination levels.

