15.4.4 Secondary Immunological Endpoints

The secondary immunological objectives for both parts of the study are:

- To evaluate IgG antibody responses induced by different vaccine doses alone or in the presence of Alhydrogel over time in healthy female volunteers:
- To determine the impact of pre-existing antibody levels on the vaccine-induced antibody response:

In addition for Part A:

- To determine the effect of Alhydrogel® adjuvant on the immunogenicity of GBS-NN vaccine
- To select the dose levels and regimens for vaccination of cohorts in Part B, based on the antibody levels at 8 weeks following the first dose (Day 57)

In addition for Part B:

- To evaluate the immune response to the GBS-NN vaccine up to 1 year following the first dose

Immunological parameters measured to evaluate objectives

In order to evaluate these objectives, GBS-NN specific IgG concentrations will be determined by ELISA against a reference standard human antibody preparation of known concentration as described in the laboratory protocol and used to derive the following parameters for each volunteer:

- Antibody concentration at each sample point ($\mu\text{g/mL}$)
- Fold increase over pre-immunisation level (Day 1) in antibody concentration at each sample point (ratio)

Specific Endpoints calculated from immunological parameters

These parameters will be used to derive the following endpoints at all time-points according to the treatment group:

- Geometric mean antibody concentration (with 95% c.i.)
- Geometric mean fold increase in antibody concentration (with 95% c.i.)
- Seroconversion rate at each sample point (proportion of volunteers with fold increase above threshold (*see below))
- At the primary immunological endpoint (Day 85) all groups in Part A will be analysed according to the proportion of volunteers whose specific antibody level ($\mu\text{g/mL}$) exceeds the following thresholds: 0.5; 1.0; 2.0; 4.0; 8.0 $\mu\text{g/mL}$. The analysis will be repeated for Part B, where the threshold values may be adjusted based on the results of Part A.

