* For Part A the threshold to define a positive response will be set arbitrarily to 2.5-fold rise above base-line, as is common practice in FIM vaccine studies. For Part B, the threshold will be set based upon the data derived from Part A. The fold increase for all 12 placebo recipients at Days 29, 43, 57 & 85 will be considered. The mean and standard deviation will be calculated and the cut-off defined as two standard deviations above the mean.

The primary immunological endpoints (still secondary study endpoint) for both Part A and Part B will be the values of these endpoints at Day 85, 12 weeks after the administration of the first dose of vaccine).

In Part A, the immunological endpoints at Days 1, 29 and 57 will be reported separately by group in a blinded fashion to enable the dose selection for Part B

Additional analyses to address objectives

For each group the individual data will be presented as scatter plots and cumulative frequency distributions at each time-point

Correlation plots will be generated to compare the specific antibody concentrations before vaccination and at 12 weeks after the first dose to evaluate the influence of pre-existing antibody levels on responses.

Statistical significance of differences in endpoint values

Statistical tests will be carried out to compare results between treatment groups, depending on studied variable type (see section inferential statistics). These analyses will be fully detailed in the SAP. In brief the following comparisons between groups will be made at Day 29 and Day 84 (and at Day 57 in Part A only):

Part A:

- Placebo group (total 12 volunteers, 6 with buffer only and 6 with alhydrogel) against all other dose groups
- Each dose level with and without Alhydrogel®
- 10µg vs 50µg, 10µg vs 250µg, 50µg vs 250µg in volunteers vaccinated with GBS-NN alone
- 10µg vs 50µg, 10µg vs 250µg, 50µg vs 250µg in volunteers vaccinated with GBS-NN in the presence of Alhydrogel
- For all groups and parameters Day 29 vs Day 85

Part B:

- Placebo group against all other dose groups (regimens to be decided)
- Group A vs Group B; Group A vs Group C; Group B vs GroupC
- For all groups and parameters Day 29 vs Day 85

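### Part A lists the Alhydrogel comparison only dose by dose (8 vs 8); a dose-adjusted pooled contrast (24 vs 24) should be added beside it

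*Combined protocol and SAP*

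**What the plan says.** Sections 7.3 and 15.4.4 give Part A a specific objective: "To determine the effect of Alhydrogel® adjuvant on the immunogenicity of GBS-NN vaccine". Section 10.1 says what the answer is for: "The effect of Alhydrogel® on these parameters will guide the decision on whether to include it in one or more cohorts in Part B".

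The layout is set out in section 10.1, "Three dose levels will be selected, with and without Alhydrogel®: A, B, and C", and in section 6.2: "Cohort 2 will receive a dose of 50µg, without Alhydrogel® and cohort 3 will receive 10µg GBS-NN with Alhydrogel"; "The 6th cohort will receive 250µg GBS-NN with Alhydrogel". Cohorts 1, 2 and 4 are 10, 50 and 250 µg without adjuvant. Cohorts 3, 5 and 6 are the same doses with it. Section 12.2.1 gives the cohort size: "There will be 10 volunteers in each group, 8 randomised to active and 2 to placebo".

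The comparison list in section 15.4.4 serves the adjuvant objective through a single entry, "Each dose level with and without Alhydrogel". Beside it stand six pairwise dose comparisons, three within each adjuvant stratum. No pooled, stratified or factorial adjuvant contrast appears, and no dose-by-adjuvant interaction. Section 15.1.3 names ANOVA only as an example, and for pre- against post-vaccination levels. It accepts that "the power of these tests for groups in Part A will be low due to small numbers of volunteers". Section 15.4.4 describes its list as brief and leaves the detail to a SAP; the text available contains no further model.

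**The concern.** The objective asks about the effect of Alhydrogel, but each listed adjuvant comparison draws its contrast from only 16 of the 48 vaccinated women. Section 15.1.3 puts low power down to small numbers. For this question, part of the loss comes from never combining the three dose-specific contrasts.

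At stake is how clearly Part A can inform the use of Alhydrogel in a Part B of up to 240 women. Three imprecise ratios, some significant and some not, would be hard to read, and the plan gives no way to summarise them.

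**Working it through.** **Inputs from the documents**
- Six cohorts (three doses, with and without Alhydrogel): sections 6.2 and 10.1.
- 8 active and 2 placebo per cohort: section 12.2.1.
- 12 placebo recipients in Part A: section 15.4.4.

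**Assumptions, because the documents give no figure**
- Two-sided alpha of 0.05, in line with the 95% intervals in section 15.4.4.
- Between-woman SD of log10 IgG of 0.5, with a range of 0.3 to 0.7.
- A common 3-fold adjuvant effect as the illustrative target.

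**Step 1: counts.** 6 x 2 = 12 placebo recipients, which reproduces the plan's figure and shows that its list is built on cohorts 1 to 6. Vaccinated women: 6 x 8 = 48, so 3 x 8 = 24 per adjuvant level. The plan states no power, so there is none to reproduce.

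**Step 2: standard errors.** Per dose: SD x sqrt(2/8) = 0.500 SD. Averaged over three doses: SD x sqrt(2/24) = 0.289 SD. The ratio is sqrt(3) = 1.73. Error degrees of freedom are 8 + 8 - 2 = 14 for a separate two-group test and 48 - 6 = 42 for a six-cell model.

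**Step 3: effect detectable with 80% power** (noncentral t). The standardised difference d converts to a fold effect as 10^(d x SD).

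| Analysis | d | SD 0.3 | SD 0.5 | SD 0.7 |
|---|---|---|---|---|
| Per dose, separate test, 14 df | 1.51 | 2.8 | 5.7 | 11.3 |
| Per dose, contrast from one model, 42 df | 1.43 | 2.7 | 5.2 | 10.1 |
| Averaged over doses, 42 df | 0.83 | 1.8 | 2.6 | 3.8 |

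With 7 evaluable active volunteers per cell, d is 1.63 for a separate per-dose test (12 df) and 0.89 for the average (36 df).

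**Step 4: power for a common 3-fold effect.** d = log10(3)/SD = 0.477/0.5 = 0.954.
- SD 0.5: 43% per dose (14 df) or 46% (42 df), against 90% averaged.
- SD 0.3: 84% or 87%, against more than 99%.
- SD 0.7: 25% or 27%, against 64%.

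**Step 5: how three separate tests would look** (SD 0.5, 14 df, treated as independent).
- All three significant: 0.428^3 = 0.078, about 8%.
- None significant: 0.572^3 = 0.187, about 19%.
- Mixed: 1 - 0.078 - 0.187 = 0.735, about 73%.
- With no adjuvant effect, at least one significant: 1 - 0.95^3 = 0.143, about 14%.

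**Step 6: where the average does worse.** If a 3-fold effect exists at one dose only, the averaged effect is 0.954/3 = 0.318 SD. The pooled test then has 19% power, against 43 to 46% for the comparison at that dose.

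**Step 7: cohort effects.** Simulation with no adjuvant effect and a random cohort effect whose SD is a stated fraction of the within-cohort SD:

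| Cohort-effect SD | Type I error, pooled | Type I error, one per-dose test |
|---|---|---|
| 0 | 5% | 5% |
| 0.2 | 9% | 8% |
| 0.3 | 13% | 13% |
| 0.5 | 26% | 24% |

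Pooling neither causes nor cures this.

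**The case against.** **The list is expressly brief.** Section 15.4.4 defers to a SAP that may contain the model. That stands: one can say that no pooled contrast is listed, not that none will be done. A reader might also infer that the plan commits to separate two-sample tests with 14 df. It does not. The list names groups to compare, and all of them could be contrasts from one 42-df model. That raises per-dose power only from 43% to 46%, because precision is still limited by 8 women per cell.

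**The decision may be dose-specific.** Section 10.1 looks for the minimum dose giving the maximum response, and asks about the adjuvant in one or more Part B cohorts. This stands too. It is a reason to keep the per-dose ratios and not let the average replace them.

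**Adjuvant is not randomised.** Volunteers are randomised to active or placebo within a cohort, and each adjuvanted cohort opens a step after its match (1 then 3, 2 then 5, 4 then 6). It would be wrong to infer that pooling is free of assumptions. The per-dose comparisons use the same cohorts and share the weakness, so it is no reason to prefer them.

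**The layout is contingent.** Sections 8.1 and 12.5 allow only one of cohorts 4 and 5 to proceed. Section 10.1 allows doses to change, and section 12.2.1 lets the number and spacing of doses vary by cohort. The contrast therefore needs a rule for unmatched cohorts.

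**No significance rule governs Part B.** Selection rests on Day 57 IgG levels and safety, and adjuvanted regimens are already anticipated. The documents do not support the inference that the Part B choice would be left undecided.

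**Conclusion.** The point holds as a cheap improvement. The documents support a complete anticipated 3 x 2 layout, a single adjuvant objective and a comparison list with no pooled adjuvant contrast. Adding one cuts the standard error by a factor of 1.73 relative to a per-dose comparison. For an effect common to all doses, at the assumed SD of 0.5, power for a 3-fold difference rises from 43 to 46% to 90%. The pooled contrast has the advantage across the whole assumed SD range.

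These sizes rest on an assumed SD, two-sided alpha of 0.05, 8 evaluable vaccinated women in every cell, an effect of similar size at each dose, and no cohort or time effect.

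A reader might take the 8% figure to mean that the three per-dose tests agree only 8% of the time. It is the chance that all three are significant. Counting the case where none is, they agree about 27% of the time (0.078 + 0.187 = 0.265 from the rounded figures; 0.266 unrounded). Nor do the documents support treating the average as the sole answer to the adjuvant question.

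**What to change.** In section 15.4.4 and the SAP, before the statistician is unblinded for the Day 57 analysis described in section 10.4:

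1. Keep the listed per-dose adjuvant comparisons.
2. Add one linear model on log IgG in the vaccinated women of cohorts 1 to 6, with dose, adjuvant and dose-by-adjuvant, at the time points already planned for Part A comparisons.
3. Report the adjuvant ratio of geometric mean concentrations, averaged over doses, with its 95% CI. Beside it, give the per-dose ratios and the interaction CI from the same model.
4. Use in the average only dose levels whose adjuvanted and unadjuvanted cohorts match in dose and booster schedule.
5. State two limits with the result. The average loses power if the adjuvant acts at one dose only. The nominal error rates of both the pooled and the per-dose tests assume no cohort or time effect, because adjuvant was not randomised between sequentially opened cohorts.

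The cost is SAP wording and a few lines of output, with no extra volunteers, samples or visits. With 8 women per cell the interaction will be estimated imprecisely, so a non-significant interaction should not be read as evidence of a common effect.

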15.4.5 Exploratory endpoints

Exploratory Objectives

[REDACTED]

[REDACTED]

16. ETHICS AND REGULATORY

16.1 Conduct

This study will be conducted in accordance with the standard operating practices of the Sponsor and CRO, which are designed to ensure adherence to Good Clinical Practice (GCP) guidelines as required by the following:

1. Declaration of Helsinki, 1964 (“Recommendations Guiding Physicians in Biomedical Research Involving Human Patients”), and all its accepted amendments to date concerning medical research in humans.
2. ICH E6 Guideline for GCP and subsequent notes for guidance (CPMP/ICH/135/95) European Agency for the Evaluation of Medicinal Products, Committee for Proprietary Medicinal Products, International Conference on Harmonisation of Pharmaceuticals for Human Use. (Note for Guidance on Good Clinical Practice, 2002).
3. European Union (EU) Clinical Trials Directive 2001/20/EC on the regulation of clinical trials in the EU and the implementation of GCP.
4. GCP Directive 2005/28/EC.

This study will be conducted in accordance with national and local laws (e.g. drug and narcotics laws) of the countries where study sites are located.

The Investigator agrees, when signing the protocol, to adhere to the instructions and procedures described in the protocol and to adhere to the principles of ICH Good Clinical Practice to which the protocol conforms as well as all governing local regulations and principles for medical research.

16.2 Review

The protocol, any protocol amendments, volunteer information sheet (VIS), informed consent form (ICF) and any study related information or documents issued to volunteers will be reviewed and approved along with other required documents by the Ethics Committee (EC) and each study site’s local EC before volunteers are screened for entry. The ECs should be constituted and functioning in accordance with ICH E6, Section 3.2, and any local regulations. The EC that provides a positive opinion for this study will be included in the clinical study report for this protocol.

A signed letter of positive opinion regarding the study from the EC Chairman must be sent to the Investigator who will provide the Sponsor with a copy. The Investigators or Sponsor will submit, depending on local regulations, periodic reports and inform the EC of any reportable AEs per ICH guidelines and local EC standards of practice.

SAEs should be reported to the EC in accordance with local regulatory requirements.

In the case of early termination/temporary halt of the study, the Investigator should notify the EC and the Sponsor should notify the Competent Authority (CA) within 15 days and a detailed written explanation of the reasons for the termination/halt should be given. If the EC decides to suspend or terminate the study, the Investigator will immediately send the notice of study suspension or termination by the EC to the Sponsor.

At the end of the study, the EC and CA will be notified within 90 days. The end of the study will be the date of the last study visit for the last volunteer in the study. The Sponsor will always also provide the EC/CA with a summary of the study's outcome.

